Official Title: The effect of topiramate on etonogestrel concentrations in contraceptive implant users

NCT Number: NCT03335163

Document date: 12/19/2017

Principal Investigator: [name] and [name]

Proposal Narrative

Objective: To evaluate the pharmacokinetic effect of concomitant topiramate therapy on etonogestrel (ENG) contraceptive implant use.

Specific Aims:

1. To evaluate the drug-drug interaction between doses of topiramate used for treatment of migraines (100-200mg per day) and the ENG contraceptive implant.
2. To evaluate the drug-drug interaction between doses of topiramate used for treatment of epilepsy (400mg per day) and the ENG contraceptive implant.
3. To characterize whether any pharmacokinetic reductions in serum ENG concentrations reach below the level needed to maintain ovulation suppression (<90pg/mL).

Rationale:

Topiramate is an anti-epileptic drug initially used for treatment of partial-onset seizures and primary generalized tonic-clonic seizures. However, its main use currently is for migraine prevention: topiramate is considered a first-line treatment for migraine prophylaxis, along with B-blockers and valproate.¹ The majority of patients afflicted by chronic migraines are reproductive age women, most of whom need reliable contraception.² Few women with chronic migraines are candidates for estrogen-containing contraceptive methods. We have recently cared for several reproductive age women taking topiramate and have found no evidence supporting or contraindicating the etonogestrel (ENG) contraceptive implant for birth control, and only scant evidence regarding drug-drug interactions between topiramate and norethindrone-containing combined oral contraceptives. As topiramate is a Pregnancy Class D drug, definitive evidence of any potential decreased efficacy of the implant is imperative. Conversely, reassuring evidence of stable ENG levels will broaden the contraceptive options for women using topiramate.

Our recent study on the effect of carbamazepine on ENG concentrations in contraceptive implant users demonstrated clinically significant reductions in serum ENG concentrations with a median decrease of 61% (range 25.4-87.2) and 8/10 participants with concentrations <90pg/mL after the intervention.³ These findings added to the limited data on the pharmacokinetic interactions between cytochrome P-450 3A4 enzyme inducers (CYP-3A4) and the ENG contraceptive implant, and will likely lead to a change in the US Medical Eligibility Criteria (MEC) for Contraceptive Use. In the MEC, carbamazepine is lumped into a broad category of “Anticonvulsant therapy” that have known CYP-3A4 induction properties.⁴ This category also includes medications such as phenytoin, barbiturates, and topiramate. Many of these medications have well documented CYP-3A4 induction properties and

consistent pharmacokinetic effects with hormonal contraceptives.⁵ Topiramate is also a CYP-3A4 inducer, but has far less pharmacokinetic data to support that its induction properties have clinical implications. There are only two small published studies that investigated topiramate's pharmacokinetic effect on a combined oral contraceptive pill. Both studies found decreases in serum estrogen concentrations with concomitant topiramate use, but no significant pharmacokinetic effect of topiramate on norethindrone concentrations.^{6,7}

The data from the norethindrone studies suggest that topiramate's pharmacokinetic effect on hormonal contraceptives differs significantly from carbamazepine, yet the MEC provides identical recommendations for these medications. Because women with chronic migraines already have limited contraceptive options, differentiating the actual interactions is crucial.

Research design and methods

Outcome Measure: Serum etonogestrel concentrations measured at baseline and then repeated after participants reach three titrated doses of topiramate:

- Visit 2 = 100mg per day
- Visit 3 = 200mg per day
- Visit 4 = 400mg per day

Description of Population to be Enrolled:

We aim to enroll subjects between 18-45 years old based on the following criteria:

Inclusion Criteria: Healthy women, who have had an ENG implant for 12-36 months at the time of enrollment and will maintain their implant during the study without modifications.

Exclusion Criteria: We will exclude women who are taking any known cytochrome P-450 3A4 enzyme inducers or inhibitors. We will also exclude women with a body mass index (BMI) <18.5, as underweight women may have altered metabolism. We will not have an upper BMI cut-off as studies have shown that overweight and obese women have equivalent metabolism and efficacy with the ENG contraceptive implant.^{8,9}

We will also exclude women with any hepatic or renal dysfunction as determined by a comprehensive metabolic panel. For purposes of this study, liver function tests will be evaluated and evidence of hepatic dysfunction will be defined as an ALT >52 or AST >39, which are beyond the reference range of normal values used by the University of Colorado clinical laboratory. Renal function will be assessed by a serum creatinine and a value >1.2 will be evidence of renal dysfunction as this is greater than the reference range used by the University of Colorado clinical laboratory.

We will also assess for any history of hepatic or renal disease to screen for diseases such as hepatitis, cirrhosis, kidney transplant, etc.

We will also exclude women with a low serum bicarbonate on screening serum electrolytes due to potential increased risk for side-effects from topiramate. We will use a cut-off of bicarbonate <21 for purposes of this study as this value is outside the reference range for the University of Colorado clinical laboratory.

Study Design

We will conduct a prospective, non-inferiority study to evaluate the pharmacokinetic effect of topiramate on serum ENG levels in contraceptive implant users. We will enroll healthy women using an ENG implant for at least 12 months and no greater than 36 months. Our exclusion and inclusion criteria are detailed as above. Interested women will undergo a phone screening prior to scheduling an enrollment visit. At the enrollment visit, potential participants will have their vital signs checked in the form of a pulse and blood pressure and will have their height and weight measured for purposes of calculating a body mass index. We will review each potential participants past medical history and current medications to ensure study eligibility. If interested participants meet our non-laboratory inclusion and exclusion criteria, then they will undergo informed consent in a private clinic room.

After the participant has been consented, we will perform a blood draw to obtain whole blood and serum. Appropriate blood samples will be sent to the University of Colorado Clinical Laboratory for a comprehensive metabolic panel. A blood sample for serum will be centrifuged on location and the serum collected for storage in our -80°F freezer. For participants that meet our laboratory exclusion criteria, we will ultimately measure a serum baseline ENG concentration from the serum collected at the enrollment visit. The research team will then follow-up the comprehensive metabolic panel to determine final eligibility based on the criteria discussed above. Eligible participants will then be given the options of either returning to our clinic to pick up the first course of the study medication or have this first course mailed to them via FedEx.

Participants will then begin a 6 week titration schedule of topiramate to a max dose of 200mg bid by the final week. Women with chronic migraines are typically treated with a dose of 100 or 200mg/day, which will be achieved in the third and fourth week of titration, respectively. The maximum recommended dose of topiramate for treatment of epilepsy is 400mg/day, which will be achieved in the sixth and final week of titration. All participants will return at the end of the third week of the topiramate titration schedule. We will then draw blood from participants at this third week visit. An appropriate blood sample will be sent to the University of Colorado Clinical Laboratory for topiramate

measurement as a measurement of compliance. Serum obtained from this blood draw will be again stored in our -80°F freezer for eventual serum ENG concentration measurement. Participants will also undergo screening for adverse events (AEs) and serious adverse events (SAEs) at this follow-up. Any participant experiencing an SAE will be removed from the study. Participants will then be given the next course of the study medication to continue the titration schedule.

All participants will return at the end of the fourth and sixth weeks to undergo identical study procedures as described for the third week visit. The final course of the study medication will be provided at the fourth week visit to continue the titration schedule through to the conclusion of the study. A topiramate level will again be measured as a measure of study compliance and serum stored for eventual serum ENG concentration measurement. At the conclusion of enrollment, all stored serum samples will be de-identified and assigned a random identification number (three letters) so that the laboratory is blinded to the timing of samples. We will then ship all samples to a Merck® laboratory for serum ENG concentration measurement. Batch analysis will be performed using a liquid chromatography mass-spectrometry method that has been previously validated. Participants will serve as their own controls for this study.

Abrupt cessation of topiramate therapy has been associated with increase in seizures in patients taking the medication for epilepsy. It is unclear if this risk is present in healthy individuals taking topiramate, but we will have participants undergo a gradual withdrawal of topiramate over 1 week after the final blood draw (end of 6 weeks). Participants will be given this withdrawal regimen at the final blood draw visit and undergo down-titration of their topiramate dose over the course of 1 week. Participants who choose to discontinue their participation early will contact the PRA or study physician for a custom down-titration schedule or abrupt discontinuation in the case of serious adverse events.

All participants will be required to use either a back-up non-hormonal method of birth control or abstain from intercourse during the study and for 4 weeks after the last dose of topiramate. Topiramate has a half-life of 21 hours, and thus, will be eliminated within 1 week of the last dose, but we will allow another 3 weeks of buffer to ensure that the ovulation has not occurred and that the contraceptive effect of the implant has reinitiated before recommending resuming unprotected intercourse.

All study visits will occur at the Comprehensive Women's Health Clinic in Lowry. This is our Family Planning site for both clinical and research visits. All consent and enrollment processes will be conducted in a private clinic room and interested participants will be allowed as much time as needed to review the consent and ask any questions regarding the consent and study procedure.

Treatment:

Etonogestrel contraceptive implant - All participants will have had an ENG implant for 12-36 months at the time of enrollment and will maintain their implant during the study without modifications.

Topiramate – Participants will undergo a 6 week titrated regimen of oral topiramate to reach a maximum dose of 400mg per day, followed by a 7-day withdrawal titration schedule, and 4 week abstinence/back-up period:

Week 1: topiramate PO 25mg daily

Week 2: topiramate PO 25mg twice daily

Week 3: topiramate PO 50mg twice daily

Week 4: topiramate PO 100mg twice daily

Week 5: topiramate PO 150mg twice daily

Week 6: topiramate PO 200mg twice daily

Week 7: withdrawal titration schedule – topiramate PO 100mg twice daily for 2 days, 100mg daily for 2 days, 50mg daily for 2 days, 25mg daily for 1 day

Week 8 – 11: abstinence/backup period

Data Analysis Plan

For this study, non-inferiority was defined as a change in serum ENG concentration that would not result in concentrations below the threshold for ovulatory suppression. We chose a non-inferiority limit of 30% because this level of decrease from the median published levels (157-207pg/mL) does not cross the probably threshold for ovulatory suppression (90pg/mL). Based on the variance findings from our carbamazepine study (SD = 67.7), we performed a sample size calculation with an alpha level of 0.05 and a beta of 0.9 for our non-inferiority limit of 30%. We used a higher beta cut-off to account for the use of a statistical sample size calculation based on a normal distribution when serum ENG concentrations has a known non-normal distribution. This calculation resulted in a sample size of 27 women. We will enroll up to 53 women to account for a potential 49% drop-out/non-compliance rate, which accounts for an expected 30% intolerance rate for topiramate doses >200mg/day. Given that this will be a repeated measures study of non-parametric data, we will use a Friedman test for our analysis. We will use a p-value of <0.05 as a cut-off for statistical significance.

Citations

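### Optional low-cost safety step: bicarbonate below 21 bars entry because of topiramate side-effects, but no bicarbonate test is listed after enrollment, so a symptomless low value would not be seen before 300 and 400 mg/day

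*Combined protocol and SAP*

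**What the plan says.** All references are to the combined protocol and SAP.

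- **Exclusion Criteria.** "We will also exclude women with a low serum bicarbonate on screening serum electrolytes due to potential increased risk for side-effects from topiramate". The threshold follows: "We will use a cut-off of bicarbonate <21 for purposes of this study". The ALT, AST and creatinine limits are explained differently, as evidence of liver or kidney dysfunction. Bicarbonate is the one laboratory criterion whose stated reason is topiramate side-effects.
- **Study Design, enrollment.** "Appropriate blood samples will be sent to the University of Colorado Clinical Laboratory for a comprehensive metabolic panel". Its use is to decide entry: "The research team will then follow-up the comprehensive metabolic panel to determine final eligibility based on the criteria discussed above".
- **Study Design, week 3.** "An appropriate blood sample will be sent to the University of Colorado Clinical Laboratory for topiramate" measurement, as a check on compliance. Serum is frozen for the later ENG assay. "Participants will also undergo screening for adverse events (AEs) and serious adverse events (SAEs) at this follow-up". Then: "Participants will then be given the next course of the study medication to continue the titration schedule".
- **Study Design, weeks 4 and 6.** Women undergo "identical study procedures as described for the third week visit". The last course of drug is supplied at week 4.
- **Treatment.** The daily dose is 100 mg in week 3, 200 mg in week 4, 300 mg in week 5 and 400 mg in week 6, followed by a one-week taper.

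**The concern.** The plan treats a bicarbonate below 21 as reason enough not to start a healthy volunteer on 25 mg/day, and gives topiramate side-effects as the reason. It lists no second look before she reaches 400 mg/day, which it describes as the maximum recommended dose for epilepsy. Adverse event screening is not described as including a laboratory test, and the frozen serum is assayed only after enrollment closes, and then for ENG. If a woman's value were below 21 at week 3 or 4 without symptoms, no listed procedure would show it and she would be given the next course.

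What is at stake is the safety of volunteers for whom the document gives no treatment purpose for topiramate. The ENG comparison is not in question.

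**Working it through.** **1. Listed bicarbonate checks against dose**

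| Time | Daily dose | Bicarbonate listed? | Drug supplied afterwards |
|---|---|---|---|
| Enrollment | none | yes, in the metabolic panel | first course, if eligible |
| End of week 3 | 100 mg | no | course for 200 mg |
| End of week 4 | 200 mg | no | course for 300 and 400 mg |
| End of week 6 | 400 mg | no | taper |

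That is one check off drug and none on drug. Weeks 3 and 4 are the visits at which a result could still alter escalation. Three dose steps remain after the week 3 draw, a rise of 400/100 = 4-fold.

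**2. Could a result arrive in time?** Assume visits on the exact day: draws on days 21 and 28, and steps to 200, 300 and 400 mg/day on days 22, 29 and 36. The documents give no turnaround for bicarbonate, so 1 to 7 days is assumed.

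- The week 3 result arrives on days 21 + 1 = 22 to 21 + 7 = 28, before day 29 (300 mg/day).
- The week 4 result arrives on days 28 + 1 = 29 to 28 + 7 = 35, before day 36 (400 mg/day).
- Each result precedes the step immediately after its draw only if it is back the same day.
- At 8 days or more, or with late visits and unchanged dosing dates, even the later steps are missed.

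**3. How many tests?** The plan's enrollment figure reproduces: 27/(1 − 0.49) = 52.9, rounded up to 53. The Data Analysis Plan allows 49% loss, including 30% intolerance of doses above 200 mg/day, which begin in week 5. The number reaching both visits depends on how those percentages combine:

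- No loss by week 4: 53 women, 53 × 2 = 106 tests.
- The 30% is a share of all enrolled, and the other 49 − 30 = 19 points all fall before week 4: 53 × 0.81 = 42.9, about 43 women and 86 tests.
- The 30% is a share of those still in the study: 0.51/0.70 = 0.729; 53 × 0.729 = 38.6, about 39 women; 38.6 × 2 = 77 tests.

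The range is therefore about 39 to 53 women and 77 to 106 tests.

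**4. Cost to Aim 2 of holding a woman below 400 mg/day.** Expected completers are 53 × 0.51 = 27.03 against 27 required, so there is no slack. Read the plan's stated beta of 0.9 as power 0.90 at n = 27. By normal approximation,

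power(n) = Φ[(z₁₋α + z₀.₉₀) × √(n/27) − z₁₋α].

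- One-sided 0.05, n = 26: (1.645 + 1.282) × 0.981 − 1.645 = 1.227, power 0.890. At n = 25, power is 0.879.
- Two-sided 0.05: power is 0.889 at n = 26 and 0.877 at n = 25.

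The cost is about 1 percentage point per woman held beyond the planned loss.

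**The case against.** The strongest objection is that a recheck helps only if bicarbonate can fall below 21 during treatment, and the documents never say that it does. The exclusion can be read as screening out women who are susceptible at baseline, with no implication for a woman who enters with a normal value. ALT, AST and creatinine are also measured only once. This largely stands. It rules out calling the gap an error and any claim about how many women would be affected. It does not remove the point: the plan's own reason for the cut-off is risk under topiramate, so a low value is relevant while she is taking the drug, whatever its cause.

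Other safeguards exist: the entry exclusions, weekly dose steps, adverse event screening at weeks 3, 4 and 6, removal for a serious adverse event, physician-arranged discontinuation, and only one week at 400 mg/day. They limit exposure. But early discontinuation is triggered by the woman's choice or a serious adverse event, not by a laboratory value.

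The document is also a short proposal narrative. A separate safety plan cannot be ruled out, so all that can be said is that no test is listed here.

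Finally, because drug is handed over at the draw visit, the fix acts late and needs call-backs. That stands and is built into the recommendation.

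**Conclusion.** The point holds as an optional, low-cost safety improvement. Within this document, bicarbonate is measured once, before any drug, and no listed procedure would detect a symptomless value below 21 before the steps to 300 and 400 mg/day.

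A reader might infer three stronger things, none of which the documents support:

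- **That the plan contradicts itself or breaks its own rule.** It does not: 21 is set as an entry cut-off, not a stopping rule.
- **That some women will develop low bicarbonate or come to harm.** No on-treatment rate or direction of change is given. The 30% intolerance figure is not linked to bicarbonate.
- **That the ENG result or the sample size is undermined.** Nothing here bears on either. The only link to power is the cost of acting on a low value.

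The timing benefit rests on exact-day visits and an assumed turnaround of about 7 days or less. The test count rests on how the 49% and 30% are combined.

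**What to change.** Add serum bicarbonate to the blood sent to the clinical laboratory at weeks 3 and 4. State in the Study Design section that:

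- the study physician reviews each result promptly and contacts any woman below 21, then decides whether to hold escalation; 21 is a trigger for review, not an automatic stop;
- the week 4 result governs both the 300 and the 400 mg/day steps, because one course covers both, with call-back where the drug is already in hand;
- the laboratory turnaround is given, with the aim of having the week 3 result before 300 mg/day and the week 4 result before 400 mg/day.

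If a separate safety plan already covers this, a cross-reference is enough. If the sponsor judges the test unnecessary, a sentence saying why would do.

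**Cost.** About 77 to 106 tests at existing blood draws, with no new visit, plus physician time and some call-backs. The documents give no price and do not say whether the topiramate sample can also serve for bicarbonate, so an extra tube may be needed. The main downside is that a woman who is held loses her 400 mg/day sample for Aim 2. Each one beyond the planned loss lowers power by about 1 point (0.90 to about 0.89 for one, 0.88 for two). Her 100 mg/day sample, and usually her 200 mg/day sample, still serve Aim 1, but a Friedman test over all four visits would leave her out.

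### The plan expects 30% intolerance above 200 mg/day, but no scheduled safety screen sees a woman on such a dose until the end of week 6; one telephone screen at the end of week 5 would close the gap cheaply.

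*Combined protocol and SAP*

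**What the plan says.** The Treatment section raises the daily dose each week: 25, 50, 100, 200, 300 and 400 mg. The fifth week is given as "Week 5: topiramate PO 150mg twice daily", that is 300 mg/day.

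Study Design sets the on-treatment visits. The first is at week 3: "All participants will return at the end of the third week of the topiramate titration schedule". Its safety content is stated: "Participants will also undergo screening for adverse events (AEs) and serious adverse events (SAEs) at this follow-up". The later visits repeat it: "All participants will return at the end of the fourth and sixth weeks to undergo identical study procedures". No visit, call or other staff-initiated contact is described at the end of week 5.

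The same section says how the last two weeks are supplied: "The final course of the study medication will be provided at the fourth week visit to continue the titration schedule through to the conclusion".

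Two safety provisions apply throughout. One is a removal rule: "Any participant experiencing an SAE will be removed from the study". The other is a route for women who stop: "Participants who choose to discontinue their participation early will contact the PRA or study physician for a custom down-titration schedule", with "custom down-titration schedule or abrupt discontinuation in the case of serious adverse events".

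The Data Analysis Plan enrols up to 53 women to allow for 49% drop-out or non-compliance. That allowance includes an expected 30% intolerance at doses above 200 mg/day.

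**The concern.** The plan names one dose range in which it expects trouble, and that range is where scheduled safety contact is sparse. A woman leaves the week-4 visit with both high-dose weeks in hand. If 300 mg/day gives her troublesome effects and she neither stops nor calls, she moves on to the maximum dose. Nobody is due to ask her about those effects until she has finished a week at 400 mg/day.

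What is at stake is the comfort and safety of healthy volunteers who have no indication for topiramate. There is a secondary point. The plan chooses a gradual withdrawal as a precaution, while saying that the risk in healthy people is unclear. A woman who quietly stops at 300 mg/day would miss the taper that a scheduled contact could arrange for her.

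**Working it through.** **The plan's own figure first.** The Data Analysis Plan gives 27 evaluable women and a 49% allowance. 27 / (1 − 0.49) = 27 / 0.51 = 52.9, rounded up to 53. The stated enrolment is reproduced.

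**Doses against screens.** Doses come from Treatment and visits from Study Design. Week *w* is taken as days 7(*w* − 1) + 1 to 7*w*, with each visit on the last day of its week.

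| Week | Daily dose (mg) | Days | Scheduled AE/SAE screen at end of week |
|---|---|---|---|
| 1 | 25 | 1–7 | none |
| 2 | 50 | 8–14 | none |
| 3 | 100 | 15–21 | day 21 |
| 4 | 200 | 22–28 | day 28 |
| 5 | 300 | 29–35 | none |
| 6 | 400 | 36–42 | day 42 |

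**Time above the plan's threshold.** Doses above 200 mg/day run from day 29 to day 42: 42 − 29 + 1 = 14 days, 7 at each dose. The screens on days 21 and 28 observe women on 100 and 200 mg/day. The only screen that observes a dose above 200 mg/day is on day 42, the last of the 14 days. The interval between screens is 42 − 28 = 14 days.

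**Steps and screens.** There are five increases. Those to 200 mg/day (day 22) and 300 mg/day (day 29) come one day after a screen. Those to 50, 100 and 400 mg/day do not. So 3 of 5 increases have no screen at the dose just below. Of the two increases that take a woman above 200 mg/day, 1 of 2 has none.

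**Do the other provisions fill the interval?** The removal rule can act only once staff know of the event. The contact sentence covers women who have decided to stop, and it relies on them to make the contact. Between days 28 and 42 neither provision creates a staff-initiated enquiry.

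**Room for lost samples.** 53 × (1 − 0.49) = 53 × 0.51 = 27.0, the stated sample size. Enrolment therefore has no slack beyond the 49% allowance.

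**The case against.** The visits are built around sampling. The Outcome Measure section defines Visits 2, 3 and 4 by the doses at which etonogestrel is measured: 100, 200 and 400 mg/day. The 300 mg/day week is a transit dose, so it has no visit. This explains the gap and is a sound reason not to add a blood draw. It does not argue against a telephone call, and the team already uses telephone screening before enrolment.

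The plan also has safeguards that deserve credit. It excludes women with hepatic or renal dysfunction, and those with low bicarbonate specifically because of topiramate side-effects. It describes 400 mg/day as the maximum recommended dose in epilepsy, so the last step stays within recommended use. That step is proportionally the smallest: 400/300 is a 33% rise, against 50% for 200 to 300 and 100% for each earlier step. Consent pages, which may tell women how to report side-effects, are not in the text available. All of this stands and keeps the priority low.

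Two stronger readings should be resisted:

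- A reader might infer that the step to 400 mg/day is a lone lapse in an otherwise screened titration. It is not: the steps to 50 and 100 mg/day are also unscreened. The contrast looks isolated only if one counts from 100 mg/day, which is not a threshold the plan uses for tolerability.
- A reader might multiply 0.30 × 53 = 15.9 and conclude that about 16 women would be helped. The 30% is part of an allowance for drop-out and non-compliance. It pools 300 and 400 mg/day. It includes women who would call to stop anyway and women who become intolerant only at 400 mg/day.

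**Conclusion.** The point holds as a modest gap in scheduled safety contact. In the dose range where the plan itself expects 30% intolerance, the first scheduled screen comes at the end of a 14-day exposure, after the step to the maximum dose.

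The documents do not support a claim that women are left without recourse: those who stop have a route to staff, and an SAE leads to removal. Nor do they show any harm to the aims or the analysis. The size of the benefit cannot be derived. It concerns women who are troubled at 300 mg/day, do not call and carry on, and no rate is given for them.

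The conclusion assumes that visits fall at the end of the stated weeks, before the next dose starts. It also assumes that no staff-initiated week-5 contact is set out in pages not available here. It does not depend on the sample size calculation.

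**What to change.** Add one scheduled telephone AE/SAE screen at the end of week 5, before the step to 400 mg/day, made by existing staff with the same questions as at the visits. An SAE leads to removal, as already planned. The study physician reviews troublesome adverse events before escalation. Any woman who stops is given the custom down-titration that the plan already offers.

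The change should stay this small: no mandatory hold, extra drug supply, extra blood draw or change to the visit dates. A compulsory hold at 300 mg/day until the call is made would go beyond the existing checks, since the plan states no hold for non-serious events at weeks 3 or 4. It would also lengthen topiramate exposure unevenly before the last etonogestrel sample, in a study of an enzyme inducer, and would leave open what happens when spare tablets run out. Under the smaller fix, a woman who is not reached simply follows the present schedule.

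The cost is at most 53 short calls, a short amendment, and possibly a few lost 400 mg/day samples for Aim 2. Only women who would otherwise have completed week 6 count as extra losses. Because enrolment has no slack, any such losses should be tracked, but a sample lost because a physician judged escalation unwise is an acceptable price.

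### The trial is called and sized as a non-inferiority study with a 30% limit, but the only named analysis, a Friedman test, never compares the fall in ENG with 30%

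*Combined protocol and SAP*

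**What the plan says.** The Study Design section states the purpose: "We will conduct a prospective, non-inferiority study to evaluate the pharmacokinetic effect of topiramate on serum ENG levels".

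The Data Analysis Plan gives a definition: "non-inferiority was defined as a change in serum ENG concentration that would not result in concentrations below the threshold for ovulatory suppression". It turns this into a margin: "We chose a non-inferiority limit of 30% because this level of decrease from the median published levels (157-207pg/mL) does not cross" the ovulatory threshold, given as 90 pg/mL. It reports a sample size of 27 for that margin and plans to "enroll up to 53 women to account for a potential 49% drop-out/non-compliance rate", a rate that includes an expected 30% intolerance above 200 mg/day.

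For the analysis it says that, because the data are repeated and non-parametric, "we will use a Friedman test for our analysis", with p<0.05 as the cut-off. No confidence bound, shifted hypothesis or other comparison with 30% is described.

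Aim 3 asks separately whether any reductions take ENG below 90 pg/mL. No summary or analysis set is given for it.

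**The concern.** The 30% limit enters the sample size and then drops out. A Friedman test asks whether the ordering of the visits within women departs from chance. It does not ask how far ENG has fallen, so the plan can be followed exactly and its main question still go unanswered.

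The conclusion matters. The Rationale says reassuring evidence would widen contraceptive options for women on topiramate. With no rule tied to the limit, a non-significant p-value could be reported as non-inferiority, or a small but consistent fall as a failure. Neither would follow.

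There is a second, smaller gap. The limit is supported at published medians, while the definition speaks of concentrations in general. A result inside the limit could be read as saying that individual women stay above 90 pg/mL. The plan requires back-up contraception or abstinence during the study and for 4 weeks after the last dose, so what is at stake is the trial's conclusion, not the protection of participants.

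**Working it through.** **1. The plan's own size.** Inputs from the Data Analysis Plan: SD 67.7, alpha 0.05, a stated beta of 0.9 (read here as power 0.90), limit 30%. The plan gives neither sidedness nor a reference level, and does not say what the SD measures. Assume one-sided alpha and the midpoint (157 + 207)/2 = 182 pg/mL, so the margin is 0.30 × 182 = 54.6 pg/mL.

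- n = 2 × (1.645 + 1.282)² × (67.7/54.6)² = 26.33, rounded up to 27.
- Enrolment: 27/(1 − 0.49) = 52.9, rounded up to 53.

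Both figures reproduce under these assumptions, so the trial can be taken as sized on the 30% limit.

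**2. What the Friedman test sees.** Take 27 women, four visits (baseline, 100, 200 and 400 mg/day), and a fall that deepens at each dose in every woman, with no within-woman noise. The rank sums are 27 × 4, 3, 2, 1 = 108, 81, 54, 27.

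- Q = 12/(27 × 4 × 5) × (108² + 81² + 54² + 27²) − 3 × 27 × 5 = 486 − 405 = 81.0, with 3 df, p = 1.9 × 10⁻¹⁷.

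Falls of 1/2/3% and of 20/40/60% both give this value. The first set is well inside 30%; the second is past it at 200 and 400 mg/day.

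**3. With noise added.** The documents give no within-woman CV, so these simulations of 27 women use assumed values.

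- CV 10%, falls of 1/2/3%: median Q about 3.3, p<0.05 in about 12% of trials. CV 10%, falls of 20/40/60%: Q about 79, p<0.05 in 100%. The results are no longer identical, but the p-value is still not a comparison with 30%.
- CV 10%, falls of 3/6/10%: Friedman is significant in 85% of trials, while a one-sided 95% bound at the last dose lies within 30% in 100%.
- CV 50%, falls of 10/20/35%: Friedman is non-significant in about 35% of trials, although the final fall exceeds the limit.

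The test can therefore mislead in either direction.

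**4. The limit at the median.** 0.70 × 157 = 109.9 and 0.70 × 207 = 144.9 pg/mL, both above 90. The fall that would reach 90 is 1 − 90/157 = 42.7% to 1 − 90/207 = 56.5%. The plan's arithmetic at the medians is right.

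**5. The limit for one woman.** A 30% fall leaves her at or above 90 only if her baseline is at least 90/0.70 = 128.6 pg/mL. The listed eligibility criteria set no minimum baseline ENG.

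How many women lie between 90 and 128.6 cannot be computed from the documents. If the between-woman SD is assumed to be 40 to 67.7 pg/mL (normal or log-normal), a uniform 30% fall newly takes 17.6–22.8% of women below 90 at a median of 157 and 0.6–8.1% at 207. For a 20% fall the range over the same medians and SDs is 0.1–11.9%.

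**6. Precision for Aim 3.** If all 27 women start at or above 90, 0 of 27 below gives an exact 95% interval of 0 to 1 − 0.025^(1/27) = 12.8%; 1 of 27 gives 0.1% to 19.0%.

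**The case against.** The strongest reply concerns the definition. A reader might infer that the plan promises no woman will fall below 90 pg/mL and that the 30% limit breaks this promise. The documents do not support that. The sentence after the definition applies 30% to published medians, so a population-median reading is natural, and step 4 shows the limit meets it with room to spare. Individual crossings are handled separately in Aim 3. What stands is a wording gap: the plan does not state the median reading, and the limit cannot support a claim about individual women.

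A reader might also infer from step 2 that Friedman always returns the same answer whatever the size of the fall. It does so only without noise, as step 3 shows. The argument needs only the weaker fact that the test contains no margin.

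The individual shares in step 5 rest on an assumed spread and on a fall exactly at the limit, where a one-sided 95% rule would pass only about 5% of trials. They are illustration. The carbamazepine study ("median decrease of 61% (range 25.4-87.2) and 8/10 participants with concentrations <90pg/mL after the intervention") shows that individual falls can vary widely, but it concerns another drug, and the Rationale itself expects topiramate to behave differently. It does not size the variation here.

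Finally, nothing in the plan says a non-significant p-value will be reported as non-inferiority. That is right. The point is that the plan provides no rule by which non-inferiority could be concluded at all.

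**Conclusion.** The point holds. A study labelled and sized as non-inferiority with a 30% limit has no analysis that uses the limit. This rests on the text alone and on what a Friedman test is; no assumed variance or baseline is needed. The Q = 81.0 comparison illustrates it under zero within-woman noise, and the simulated rates depend on assumed CVs.

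The secondary point is a clarification. The limit is adequate for the population median over the published range and says nothing firm about individuals below 128.6 pg/mL at baseline. That crossing value needs only the 90 pg/mL threshold and a 30% fall; how many women it affects is unknown. The missing Aim 3 summary is a lesser gap. The change should be made, since the trial's main conclusion depends on it.

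**What to change.** 1. **Test against the limit.** At each dose (100, 200, 400 mg/day), form the within-woman ratio of ENG to baseline. Conclude non-inferiority at that dose only if the lower one-sided 95% confidence bound on the ratio is above 0.70. State the one-sided 0.05 level, since the plan gives no sidedness. Name one method as primary in advance: a Hodges–Lehmann estimate with signed-rank bound on log ratios, which suits the plan's stated non-normality, or a paired t bound on log ratios (geometric mean ratio). Report each dose as its own conclusion; a claim for the whole 100–200 mg range of Aim 1 requires both doses to pass. Keep Friedman as a secondary test of any change.

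2. **Fix the analysis set.** Use women with a baseline and a sample at that dose who are compliant by topiramate level, which is already collected ("A topiramate level will again be measured as a measure of study compliance"). Set the cut-off before ENG results are known; batch assay after enrolment ends makes this feasible. Repeat in all sampled women. The 27 is the number left after the full 49% loss, so the sets at 100 and 200 mg should be larger.

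3. **Clarify the definition.** State that it refers to the population median, check the trial's own baseline median against 128.6 pg/mL, and make no claim from the 30% limit alone that individual women stay above 90.

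4. **Aim 3.** Per dose, report the number and proportion falling below 90 among women with baseline at or above 90, with an exact 95% interval. List women below 90 at baseline separately. This is descriptive, with no pass level.

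**Cost.** Plan wording, one bound per dose and one table, with no new samples or visits. With 27 women and a paired t bound, the re-run simulations pass when there is no true fall in 99.3% of trials at CV 30% and 80.3% at CV 50%; with a true 10% fall, in 91.3% and 56.7%. Power is therefore adequate unless within-woman variation is large. The permitted claim becomes less favourable, and the Aim 3 proportion stays imprecise (0 of 27 still allows up to 12.8%, and more if fewer women start at or above 90).
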